Appendix D: Clinic Variables Checklist

EXTRA-CVD

Clinic Variables Checklist

Date: _____

Study site (circle one): UH/SIU MetroHealth Duke

Instructions: For each of the following support services, please circle the option that best describes availability of that services in your ID or HIV clinic.

Resources	Not Available	Same Day Availability	Available by Advance Scheduling/Request Only
Adherence Support Services (Ex. Assisted pill box filling, DOTS, etc.)	0	1	2
CVD Prevention Specialist/Consultant with HIV Expertise	0	1	2
Dietician/Nutritionist	0	1	2
Exercise or Fitness Classes	0	1	2
Medication Adherence Incentive Programs	0	1	2
Nurse Support Line	0	1	2
Peer Coaching	0	1	2
Pharmacist	0	1	2
Social Worker Led Support Group(s)	0	1	2
Tobacco Cessation Program	0	1	2
Transportation Vouchers	0	1	2

What additional in-clinic resources are available to aid patients in managing their hypertension and/or hyperlipidemia?

Appendix E: PLHIV Pilot Participant Acceptability Testing Guide

Note: Not all questions will be asked explicitly. Participants may answer the questions, or cover the topic, in the course of the one-on-one conversation.

Study background

Welcome to our discussion! People living with HIV (PLHIV) are at increased risk for heart disease; however, the uptake of evidence based therapies to prevent heart disease is substandard. As such, strategies to improve the uptake of cardiovascular disease preventive therapies among PLHIVs are urgently needed. The goal of this study is to test a prevention, nurse-led intervention to extend the HIV/AIDS treatment cascade for the treatment of hypertension and high cholesterol among PLHIV on suppressive antiretroviral therapy.

Introduction

[Remind about Audio Recording and not to use real names]

Thank you for talking with me today. I am interested in learning more about your thoughts and beliefs about cardiovascular disease among your HIV+ patients. I am most interested in your thoughts about a new intervention our research team is planning on scaling-up at your clinic and for your HIV+ patients who have hypertension and high cholesterol. I am going to ask you some questions about these topics to hear about your experiences and perspectives. Please know that there is no right or wrong answer.

Here are the ground rules for our focus group discussion. We would like to have everyone participate in this discussion. I will only give you all a few probes and would like for you all to react to those probes. Beyond giving the probes, the discussion will be entirely driven by you all – my only job is to facilitate. And I will facilitate to get more clarity on statements you all share. Additionally, I am interested in engaging each of you to talk freely and to make sure everyone has equal opportunities to speak. My main purpose here is to ask questions, listen, and make sure that you have the opportunity to share your thoughts and perspectives. This session is being recorded, as was noted in the consent form you signed before, so that none of your informative comments and feedback will be missed. Again your names will not be collected and your comments will be confidential. Finally, you are under no obligation to talk about anything that you are not comfortable discussing with me. Do you have any questions or concerns before we begin?

[Facilitator, please note the participant's ID number in the audio recording so we can match it to the demographic information.]

Intervention Acceptability

Finally, we are interested in a new initiative, with a new nurse coordinator - led intervention, that we designed to help patients like you reduce their risk of heart disease in clinics around the

country. As such we would like to get your opinion on thoughts on this intervention. As a reminder, all information you provide will be confidential and aggregated across three clinics.

Facilitators and barriers to the nurse-led intervention for HIV+ patients with hypertension and high cholesterol

1. Please tell me your thoughts on working with your CVD nurse to tailor treatment for HIV+ patients like yourself who have either been diagnosed with hypertension and high cholesterol.
 - a. PROBE: What general experience do you have working with nurses to manage your health?
2. What do you think are some potential benefits or barriers of working with nurses?

[Interviewer will share the refined intervention structure and format with the participant(s).]

Thoughts on logistical factors (i.e. resources or tools at that clinic)

3. What are your initial thoughts on this intervention?
4. Do you like this intervention?
5. Please tell me any potential concerns you may have as an HIV+ patient participating in this intervention?
6. What are some potential benefits that you see with integrating this intervention into your current treatment?
7. What are some current resources or tools within your clinic that you think will help facilitate the integration of this intervention for your care?
 - a. Conversely, what may be some aspects of your clinic that you think will be a barrier to integrating this intervention for your care or treatment?
8. Do you feel that this intervention is relevant in terms of your health or the issues you are dealing with?
9. Would you be interested in having this service offered to you as part of your treatment?

Secondary/Follow-up Questions

Follow-up “Probes” after significant statements are made:

[Earlier/A moment ago/when you first started speaking/when you were talking about x] you said [significant statement].

- Can you tell me more about that?
- Can you tell me more about how that affects [X]
- Can you clarify what you mean by [significant statement]
- Can you give me an example of a time when [significant statement] happened to you

Conclusion

Is there anything else you want us to know about [X]? (YES return to interview; NO proceed)

We want to thank you so much for your participation and remind you that everything we have discussed will remain private. The audio file will be destroyed once this interview is transcribed, and the transcription will not contain your name or any identifying information.

Appendix F: PLHIV Pilot Participant Feasibility Testing Guide

Note: Not all questions will be asked explicitly. Participants may answer the questions, or cover the topic, in the course of the one-on-one conversation.

Study background

Welcome to our discussion! People living with HIV (PLHIV) are at increased risk of heart disease; however, the use of the most effective treatment options or approaches to manage heart disease in this population is not the best. As such, strategies to improve the uptake of heart disease prevention among PLHIVs is very important and needed in HIV clinics. The goal of this study is to test a prevention, nurse-led intervention to extend the HIV/AIDS treatment cascade for the treatment of hypertension and high cholesterol among PLHIV on suppressive antiretroviral therapy.

Introduction

[Remind about Audio Recording and not to use real names]

Thank you for talking with me today. I am interested in learning more about your thoughts and beliefs about cardiovascular disease among your HIV+ patients. I am most interested in your thoughts about a new intervention our research team is planning on scaling-up at your clinic and for your HIV+ patients who have hypertension and high cholesterol. I am going to ask you some questions about these topics to hear about your experiences and perspectives. Please know that there is no right or wrong answer.

Here are the ground rules for our focus group discussion. We would like to have everyone participate in this discussion. I will only give you all a few probes and would like for you all to react to those probes. Beyond giving the probes, the discussion will be entirely driven by you all – my only job is to facilitate. And I will facilitate to get more clarity on statements you all share. Additionally, I am interested in engaging each of you to talk freely and to make sure everyone has equal opportunities to speak. My main purpose here is to ask questions, listen, and make sure that you have the opportunity to share your thoughts and perspectives. This session is being recorded, as was noted in the consent form you signed before, so that none of your informative comments and feedback will be missed. Again your names will not be collected and your comments will be confidential. Finally, you are under no obligation to talk about anything that you are not comfortable discussing with me. Do you have any questions or concerns before we begin?

[Facilitator, please note the participant's ID number in the audio recording so we can match it to the demographic information.]

Intervention Feasibility

We are interested your experience and thoughts have participated in the pilot test for the new nurse coordinator-led intervention that we designed to help your patients reduce their risk of heart disease in clinics around the country. As a reminder, all information you provide will be confidential and aggregated across three clinics.

Participating in the nurse-led intervention for HIV+ patients with hypertension and high cholesterol:

1. Please tell me what your general thoughts and experience was with the nurse-led intervention?
2. What effect (positive or otherwise) did the intervention have on how you engaged with the following providers:
 - a. Prevention nurse: How did you interactions with the nurse evolve over the course of the 6-week pilot?
 - b. Your primary HIV nurse: Did your participation in this pilot affect your relationship with your primary HIV nurse? If so, how?
 - c. Your physician providers: How did your participation in this pilot affect your relationship with your primary HIV doctor and/or your primary care doctor?
3. After meeting with your nurse during the intervention what differences did you notice in how you responded to your own treatment?
 - a. PROBE: How where you better able to treat or care for your hypertension and cholesterol?

Thoughts on intervention's feasibility

4. How do you feel this intervention fits within your clinic setting?
5. After completing all of the intervention-related meetings with the nurse, what barriers did you feel that they faced in helping you manage your hypertension and cholesterol?
6. In what ways do you think this intervention, in its current form, will be an effective tool or resource for your clinic to integrate going forward?
7. In what ways do you think this intervention, in its current form, will NOT be an effective tool or resource for your clinic to integrate going forward?
8. What feedback have you shared or provided about the intervention with the clinic supervisors or nurses?
9. Does this intervention seem possible as a form of HIV treatment or management for people with hypertension and high cholesterol?
10. How do you think this intervention can be implemented within general HIV care clinics?

Secondary/Follow-up Questions

Follow-up "Probes" after significant statements are made:

[Earlier/A moment ago/when you first started speaking/when you were talking about x] you said [significant statement].

- Can you tell me more about that?
- Can you tell me more about how that affects [X]
- Can you clarify what you mean by [significant statement]
- Can you give me an example of a time when [significant statement] happened to you

Conclusion

Is there anything else you want us to know about [X]? (YES return to interview; NO proceed)

We want to thank you so much for your participation and remind you that everything we have discussed will remain private. The audio file will be destroyed once this interview is transcribed, and the transcription will not contain your name or any identifying information.

Appendix G: Health Worker Feasibility Testing Guide

Note: Not all questions will be asked explicitly. Participants may answer the questions, or cover the topic, in the course of the one-on-one conversation.

Study background

Welcome to our discussion! People living with HIV (PLHIV) are at increased risk for heart disease; however, the uptake of evidence based therapies to prevent heart disease is substandard. As such, strategies to improve the uptake of cardiovascular disease preventive therapies among PLHIVs are urgently needed. The goal of this study is to test a prevention, nurse-led intervention to extend the HIV/AIDS treatment cascade for the treatment of hypertension and high cholesterol among PLHIV on suppressive antiretroviral therapy.

Introduction

[Remind about Audio Recording and not to use real names]

Thank you for talking with me today. I am interested in learning more about your thoughts and beliefs about cardiovascular disease among your HIV+ patients. I am most interested in your thoughts about a new intervention our research team is planning on scaling-up at your clinic and for your HIV+ patients who either have or at risk for CVD. I am going to ask you some questions about these topics to hear about your experiences and perspectives. Please know that there is no right or wrong answer.

Here are the ground rules for this semi-structured interview. I am going to ask you a few questions and will only give you a few probes with the intention that you will react to those probes. Beyond giving the probes, the discussion will be entirely driven by your responses – my only job is to facilitate. And I will facilitate to get more clarity on statements you share. Additionally, I am interested in engaging each you to talk freely and to make sure you are able to share your thoughts fully. My main purpose here is to ask questions, listen, and make sure that you have the opportunity to share your thoughts and perspectives. This session is being recorded, as was noted in the consent form you signed before, so that none of your informative comments and feedback will be missed. Again your name will not be collected and your comments will be confidential. Finally, you are under no obligation to talk about anything that you are not comfortable discussing with me. Do you have any questions or concerns before we begin?

[Facilitator, please note the participant's ID number in the audio recording so we can match it to the demographic information.]

Intervention Feasibility

We are interested your experience and thoughts have participated in the pilot test for the new nurse coordinator-led intervention that we designed to help your patients reduce their risk of heart disease in clinics around the country. As a reminder, all information you provide will be confidential and aggregated across three clinics.

Participating in the nurse-led intervention for HIV+ patients with hypertension and cholesterol

1. Please tell me about your thoughts and experience with the nurse-led intervention?
2. How did the intervention impact (positive or otherwise) the way in which you engaged with HIV+ patients?

3. Did you feel prepared to integrate the intervention in your current treatment routine? If so, how? If not, what would have helped you to be more prepared?
4. After meeting with your patients during the intervention, what were some differences you noticed in how patients responded to their treatment?
 - a. PROBE: How were patients better able to treat or care for their CVD risks?

Thoughts on the intervention's feasibility

5. How do you feel this intervention fits within your clinic setting?
6. After completing all of the intervention procedures with your patients, did you feel that they still faced any barriers to managing their hypertension and cholesterol?
7. How did this intervention impact your workload with treating HIV+ patients?
8. In what ways do you think this intervention, in its current form, will be an effective tool or resource for your clinic to integrate going forward? In other words, what worked well in this intervention in this particular setting?
9. In what ways do you think this intervention, in its current form, will NOT be an effective tool or resource for your clinic to integrate going forward? Or what can be improved?
10. What feedback have you shared or provided about the intervention with your clinic colleagues?
11. Does this intervention seem possible as a form of HIV treatment or management for people with hypertension and high cholesterol?
12. How do you think this intervention can be implemented within general HIV care clinics?

Secondary/Follow-up Questions

Follow-up "Probes" after significant statements are made:

[Earlier/A moment ago/when you first started speaking/when you were talking about x] you said [significant statement].

- Can you tell me more about that?
- Can you tell me more about how that affects [X]
- Can you clarify what you mean by [significant statement]
- Can you give me an example of a time when [significant statement] happened to you

Conclusion

Is there anything else you want us to know about [X]? (YES return to interview; NO proceed)

We want to thank you so much for your participation and remind you that everything we have discussed will remain private. The audio file will be destroyed once this interview is transcribed, and the transcription will not contain your name or any identifying information.

Appendix H: Design Team Discussion Guide

Themes to be assessed:

- Previous design team experience.
- Understanding of the design team approach.
- Thoughts on the design team process for the nurse-led intervention.
- Experience for each phase or meeting of the design approach.
- Thoughts on the final intervention model.

General focus group discussion introduction:

For this part of our design team meeting, I am most interested in learning more about your thoughts and beliefs about the human-centered design process. I am going to ask you some questions about the process to hear about your experiences and perspectives. Please know that there is no right or wrong answer.

Here are the ground rules for our focus group discussion. We would like to have everyone participate in this discussion. I will only give you all a few probes and would like for you all to react to those probes. Beyond giving the probes, the discussion will be entirely driven by you all – my only job is to facilitate. And I will facilitate to get more clarity on statements you all share. Additionally, I am interested in engaging each of you to talk freely and to make sure everyone has equal opportunities to speak. My main purpose here is to ask questions, listen, and make sure that you have the opportunity to share your thoughts and perspectives. This session is being recorded, as was noted in the consent form you signed before, so that none of your informative comments and feedback will be missed. Again your names will not be collected and your comments will be kept confidential, not to be revealed to anyone outside of this room. Finally, you are under no obligation to talk about anything that you are not comfortable discussing with me. Do you have any questions or concerns before we begin?

Focus group questions

- What impact do you think your individual participation in the design team had on the final intervention model?
- Tell me about your experiences working on a team with individuals from different professions and roles?
- What was your personal contribution and the overall team's contribution to the design team?
- Was there a particular design phase (i.e. brainstorming, conceptualization, creation, iteration I, or iteration II) that you found to be most insightful for the entire design experience? Why or why not?
- Which design phase (i.e. brainstorming, conceptualization, creation, iteration I, or iteration II) did you find to be most challenging and why do you think so?
- Which design phase (i.e. brainstorming, conceptualization, creation, iteration I, or iteration II) did you find to be least challenging and why do you think so?

- What are your general thoughts on the final intervention model? Do you think that this version will meet the intended goals of our design team and that of the research study?
- Are there any closing thoughts that you want to share or that you think we should have discussed in terms of the final intervention model that we do not touch on?
- Are there any final thoughts that you want to share or that you think we should have discussed in terms of the design team experience that we do not touch on?

Thank you for your time and participation. We very much appreciate your comments, discussions, and input throughout the design process.

Appendix I: Trust and Communication Survey (PLHIV participant – Provider)

As a participant in the EXTRA-CVD study, we are asking you to complete a survey about your relationship with your healthcare providers. You will need at least 15 minutes of uninterrupted time to take this survey. If you have any questions, please see your EXTRA-CVD nurse or study coordinator. Please understand that your answers will be confidential. More specifically, your name and the names of your providers will never be recorded with your data. The unique ID numbers will be kept separately by study staff at your site who do not have access to the survey results. Please respond below in order to proceed:

- Yes I understand my rights as a participant in this study. I consent to proceed.
- No I do not consent and will not participate in this study and survey

Please enter here your unique participant ID. EXTRA-CVD study staff will ensure that you enter your correct ID. PLEASE DO NOT LIST YOUR NAME.

Please select which visit you completed today as part of this study. EXTRA-CVD study staff will ensure that you select the correct answer.

- Baseline visit
- 4 months visit
- 8 months visit
- 12 months visit

As a participant of this study, in the following sections, you will be asked some questions regarding your relationships with providers that may help treat your HIV or your blood pressure and cholesterol. At a minimum, this will include: your HIV provider and your EXTRA-CVD nurse.

Additionally, you may be asked some questions about the rest of your health care providers (for example, your Primary care physician, your HIV clinic nurse or you Non-HIV specialists).

Protocol

We hope to collect quality data for our research. But If you feel uncomfortable to answer any of the questions or feel that a question is not applicable to you, feel free to skip it.

Do you have a HIV clinic nurse?

Yes

No

Do you have a Primary care physician?

Yes

No

Please indicate which of the following medical professionals primarily treats your blood pressure (if multiple physicians care equally for your blood pressure, please select all that apply):

My HIV provider

My HIV clinic nurse

My Primary care physician

My Non-HIV specialist, please specify the specialist type (i.e.; cardiologist, nephrologist, endocrinologist): _____

No one manages my blood pressure

Please indicate which of the following medical professionals primarily treats your cholesterol (if multiple physicians care equally for your cholesterol, please select all that apply):

My HIV provider

My HIV clinic nurse

My Primary care physician

The same Non-HIV specialist who also treats my blood cholesterol (as indicated in the question above)

A different Non-HIV specialist from whom treats my blood cholesterol as indicated in the prior question), please then specify the specialist type- i.e. cardiologist, nephrologist, endocrinologist): _____

No one manages my cholesterol

*** The participant will complete the following survey items for each of their providers identified above.

Please think of your relationship with your [HIV, PCP, non-HIV specialist] provider. For the validity of this study, please answer honestly. Recall your answers are confidential and will never be shared with this provider nor anyone else outside our research team. Some of the questions may sound repetitive, please do read fully before answering each question.

How long have you been a patient of this provider?

- I just became a patient this past month
- Less than 6 months
- 6 months to 1 year
- 1-2 years
- 3-5 years
- More than 5 years

How often do you communicate with this provider?

- Every 1-2 months
- Every 3-4 months

Protocol

Every 5-6 months

Once yearly

Please rate the following statements based on your recent visits with this provider and overall care with this provider.

	Strongly Disagree	Disagree	Neither Agree nor Disagree	Agree	Strongly Agree
My provider has much knowledge about the treatment that needs to be done.					
My provider is very concerned about my welfare.					
I feel I can discuss with my provider how I honestly feel about my health treatment, even negative feelings and frustration.					
Overall, I trust my provider.					

	Strongly Disagree	Disagree	Neither Agree nor Disagree	Agree	Strongly Agree
My provider and I communicate effectively.					
My provider listens carefully to me.					
Overall, I am satisfied with the communication with my provider.					

Protocol

	Strongly Disagree	Disagree	Neither Agree nor Disagree	Agree	Strongly Agree
My provider and I have a good relationship.					
I feel part of a team with my provider in regards to my health care and needs.					
Overall, I like my provider.					
Overall, I am satisfied with my provider.					

Do you have any recommendations to improve your care experience with this provider?

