1. Care coordination. Beginning with initial enrollment, the prevention nurse will coordinate blood pressure and cholesterol management for all participants in the intervention arm. Care coordination will consist of tailored discussions with the participant and his/her providers about which provider will take primary responsibility for BP and cholesterol management. Considerations of patient-provider trust and provider comfort level or experience will inform this decision. The prevention nurse will direct subsequent management decisions to the designated provider but will facilitate communication by notifying the non-designated of any changes to medications.

At the baseline visit, the prevention nurse will map the participant’s care team and communication preferences, to ensure that all providers in the patient’s care team are accounted for. After the initial visit, the nurse will contact members of the participant’s care team through normal clinical communication channels which are standard of care for that clinic site (e.g. EMR messages, email, phone) to inform them that the participant has been enrolled in the study. The prevention nurse may use this opportunity to discuss any potential modification to suggested blood pressure and cholesterol targets.

In order to better incorporate the prevention nurse into clinic workflow, a number of recommendations were made by the design teams. These include having nurse meet & greet and regular staff updates on the study to ensure that communication preferences are respected.

Component 1—Relevant process evaluation data for aim 3: (1) number and duration of telephone calls and emails to providers or providers’ staff; (2) number and nature of communication notes

in EMR; (3) prevention nurse trust & communication ties with providers; (4) time spent coordinating care.

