2. The prevention nurse at each site will keep a key of unique identifiers for each provider within a patient's care team network. The prevention nurse will keep this in a password protected file on his/her own personal network drive (to ensure that it is backed-up). The prevention nurse will be the only one with access to this file.
 3. The nurse will prepare the participant who is taking the survey by helping the participant enter the unique identifier for his/her HIV provider, HIV-nurse, primary care provider, or non-HIV specialist. The participant will then complete the same set of survey questions for each of his/her providers.
 4. On a quarterly basis, or when not fewer than 10 complete records have accumulated, the UH/Case Western study coordinator will compile the survey data and link it to exported RedCap data using a statistics software program (STATA 13.0).
 5. This completely deidentified dataset will then be sent to two consultants with expertise in social network analysis ([name], UT Dallas and [name], U North Texas) who will conduct the analyses.
 6. Results will be reported anonymously by site (site A, B, and C), prevention RN (RN1, RN2, RN3) and provider (HIV provider 1, PCP 1, etc...).

Analyses: The primary analysis will be to test the intervention effect on PLHIV-Provider trust and communication ties, using a similar repeated measures analysis as described below for the primary BP and secondary cholesterol outcomes. As an exploratory analysis, we will assess whether the effect of the EXTRA-CVD intervention on the primary BP and secondary non-HDL outcomes are mediated by changes in trust and communication ties. Additional exploratory analyses will be conducted to assess the effect on the balance of trust/communication ties between HIV vs. non-HIV providers and to assess the longitudinal change in prevention RN-provider trust and communication over the course of the intervention.

Aim 4 Procedures:

Intervention Adaptation

The intervention will be adapted with the assistance of stakeholder design teams that have already been convened in Cleveland and Durham as part of our original intervention adaptation sub-aim 1.1. We now propose an additional round of design iteration to make virtual adaptations for this aim. Members of both design teams will be invited to attend combined virtual design sessions hosted in Zoom.

Adaptation Description

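### In Appendix I both specialist answers to the cholesterol question refer back to cholesterol instead of blood pressure, so a second non-HIV specialist may go unlisted and unrated

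*Combined protocol and SAP*

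**What the plan says.** Appendix I (participant–provider survey) asks whether the participant has an HIV clinic nurse, and then "Do you have a Primary care physician". It goes on to "Please indicate which of the following medical professionals primarily treats your blood pressure", with a non-HIV specialist among the answers and a space for the type of specialist. A parallel question on cholesterol follows, with two specialist answers. One of them reads "The same Non-HIV specialist who also treats my blood cholesterol (as indicated in the question above" and has no space for a specialist type. Its counterpart, which does ask for the type, reads "A different Non-HIV specialist from whom treats my blood cholesterol as indicated in the prior question".

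More than one box may be ticked in the cholesterol item, on the condition "if multiple physicians care equally for your cholesterol, please select all that apply". The form then states: "The participant will complete the following survey items for each of their providers identified above".

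The Aim 3 procedures (PLHIV-Provider Trust & Communication Ties) are broader. There the participant survey covers all members of the care team, and the nurse helps enter an identifier for each provider, with non-HIV specialists named among them. The main analysis of this component tests the intervention effect on ties. Exploratory analyses test whether ties mediate the BP and non-HDL effects, and also "assess the effect on the balance of trust/communication ties between HIV vs. non-HIV providers".

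In the intervention arm, care coordination includes discussing "which provider will take primary responsibility for BP and cholesterol management", informed by patient–provider trust among other things. Referrals to BP or cholesterol specialists are a counted process measure of the medication component.

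**The concern.** The cholesterol item is not background text. Its answers help decide which specialists are listed, and listing decides who is rated. The item needs to learn whether the cholesterol specialist is the same person as the blood pressure specialist. As printed, it compares the cholesterol specialist with the cholesterol specialist.

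If a participant answers as worded, a second specialist can vanish from the data. Non-HIV specialists are also the group least protected against this, because they have no yes/no item of their own. The analysis of balance between HIV and non-HIV providers is therefore the most exposed.

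**Working it through.** The documents give no figure for this point, so there is nothing to reproduce. The check compares the texts and enumerates cases by hand.

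**Step 1. What each option means.** Let A be a specialist for blood pressure and B a different specialist for cholesterol. With 'blood pressure' in both options, 'same' means that the cholesterol specialist is A, and 'different' means that it is not A. With 'blood cholesterol' as printed, 'same' describes anyone who treats cholesterol, while 'different' describes a cholesterol specialist who is not the one treating cholesterol, which is impossible.

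**Step 2. Distinct specialists recorded, by true situation.**

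| True situation | Intended wording | Literal reading of printed wording |
|---|---|---|
| No specialist | 0 | 0 |
| A for blood pressure only | 1 | 1 |
| A for both | 1 | 1 |
| A for blood pressure, B for cholesterol | 2 | 1 |
| B for cholesterol only | 1 | 0 or 1, depending on coding |

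Three of the five situations are unaffected. In the fourth, the loss is 2 − 1 = 1 specialist. In the fifth, a 'same' tick has no blood pressure specialist to refer to, so the loss is 0 or 1. In both of these rows the type of B is not captured, because only the 'different' option asks for it. Any error from literal reading is an undercount.

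**Step 3. Who can be listed at all.** The HIV provider and the study nurse are always included. The HIV clinic nurse and the PCP have yes/no items. A non-HIV specialist enters the printed form only by being named as a main, or equally involved, treater of blood pressure or cholesterol. The Aim 3 text carries no such limit, so form and text disagree.

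**Step 4. Can the intervention change the listing?** Yes, in principle. Discussions about responsibility and specialist referrals are parts of the intervention, and both bear on who counts as the main treater after baseline. The documents give no rule for a set of rated providers that changes after randomization.

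**Step 5. Where the data go.** They feed the between-arm tie analysis, the mediation analysis and the balance analysis, all in Aim 3. The mixed models for systolic BP and non-HDL in the SAP do not use these items.

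**The case against.** The strongest reply is that this is a slip most people will read through. The options are plainly contrasted as 'same' and 'different', both point to the preceding question, and participants are told to ask the nurse or coordinator if unsure. The nurse helps enter a unique identifier for each provider, so two specialists who are both rated carry different identifiers. The survey runs in Qualtrics, and its branching is not visible in the printed form. All of this stands as mitigation. What it cannot do is bring back a specialist who was never listed.

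Four stronger readings are tempting, and the documents do not support them:

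- *Specialist ties are miscounted.* This is a risk of unknown frequency. Nothing shows how many participants have separate specialists or read the item literally.
- *The different situations are indistinguishable in the data.* A cholesterol-only specialist can be detected by comparing the two items: a 'same' tick with no specialist ticked for blood pressure stands out.
- *The nurse decides who is responsible and so selects who is rated.* Care coordination is described as discussion with the participant and the providers.
- *Selective loss of low-trust ties inflates trust in one arm by a calculable amount.* That would require assuming one-arm loss of exactly the least-trusted specialists, for which there is no basis. It would also concern the mean over specialist ties only, not the arm mean over all rated providers.

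A changed provider set is also not bias in itself. Specialist ties gained or lost may be part of what the balance analysis is meant to detect.

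**Conclusion.** The wording is wrong in both specialist options, and the item affects who is rated. Read literally, it lists one specialist instead of two when blood pressure and cholesterol are treated by different non-HIV specialists, and the second specialist's type is lost. This assumes that the participant follows the printed words and that staff do not catch the mismatch. The documents give no frequency for either, so no overall size can be computed.

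The secondary point is a gap rather than a demonstrated bias. The form lists specialists more narrowly than the Aim 3 text promises, the intervention can alter that listing, and no analysis rule separates a change in who is rated from a change in tie strength. The consequences stay within Aim 3.

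**What to change.** **Wording.** Replace 'blood cholesterol' with 'blood pressure' in both specialist options of the cholesterol item. This is one word in each. Record the date of the change, because repeated measures will straddle it.

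**Surveys already collected.** State the printed wording in the report. Cross-check the specialist ticks in the two items against the provider identifiers, looking for a 'same' tick with no blood pressure specialist and for a 'same' tick alongside two specialist identifiers. This can be done on identifiers alone, without names.

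**Listing.** Reconcile the form with the Aim 3 text, for example with a yes/no item for a non-HIV specialist next to those for the HIV clinic nurse and the PCP. The cost is one item, plus one extra block of ratings for some participants.

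**Analysis.** Keep the analysis of currently listed providers, and report beside it a sensitivity analysis restricted to providers named at baseline. The baseline set should not replace the current set: newly formed ties may be part of the effect, and a provider no longer seen may not be ratable. Where a baseline provider was re-rated, no new data are needed. The survey schedule should be settled at the same time, since the Aim 2 text gives 0 and 12 months while the Aim 3 text has every in-person visit.
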